4.7.2 Components of Primary Endpoint

The time to first occurrence of each of the five component events of the primary endpoint will be analyzed by the same methods described for the primary endpoint. Kaplan-Meier

estimates, the log-rank test stratified by stratification factors used at randomization, and the Cox proportional hazards model including the stratification factors as specified above for the primary efficacy endpoint, will be summarized by treatment group. Kaplan-Meier curves stratified by each stratification factor will be presented. These analyses will be conducted for the ITT, mITT and PP populations.

Similarly, the rules for determining date of event/date of censoring for the primary efficacy endpoint (Section 4.7.1) will be applied to the components of primary endpoints. For the CV death endpoint, patients who do not die from CV causes will be censored at death from non-CV causes or last visit/phone contact as described in Section 4.7.1.1. For all other events (nonfatal MI [including silent MI], nonfatal stroke, coronary revascularization, and hospitalization for unstable angina determined to be caused by myocardial ischemia by invasive/non-invasive testing), patients who do not experience the event will be censored at death or last visit/phone contact, consistent with that described in Section 4.7.1.1.

In addition, a recurrent event analysis using Andersen-Gill and Li-Lagakos methods will be carried out for the individual primary event constituents other than CV death.

4.7.3 Analysis of Secondary Efficacy Endpoints

The key secondary hypothesis will be tested as part of the confirmatory process only if the primary analysis is statistically significant. For the analysis of secondary efficacy endpoints, the Type 1 error will be controlled by testing each endpoint sequentially, starting with the key endpoint. Testing will be done at a significance level consistent with that used for the primary endpoint and will cease when a secondary endpoint is found for which treatments do not significantly differ. P-values will be presented for all analyses, but they will be considered descriptive after the first non-significant result is obtained.

Each of the secondary endpoints will be analyzed by the same methods described for the primary efficacy endpoint. Kaplan-Meier estimates, the log-rank test stratified by stratification factors used at randomization, and the Cox proportional hazards model including the stratification factors as specified above for the primary efficacy endpoint, will be summarized by treatment group. Kaplan-Meier curves stratified by each stratification factor will be presented. Similarly, the rules for determining date of event/date of censoring for the primary efficacy endpoint (Section 4.7.1) will be applied to the secondary endpoints. These analyses will be conducted for the ITT population.

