12.2.4.3. Secondary Endpoint Analyses

The key and other secondary endpoints are listed in [Section 9.2.2](#). The key secondary hypothesis will be tested as part of the confirmatory process only if the primary analysis is statistically significant. For the analysis of secondary efficacy endpoints, the Type 1 error will be controlled by testing each endpoint sequentially, starting with the key endpoint. Testing will be done at a significance level consistent with that used for the primary endpoint and will cease when a secondary endpoint is found for which treatments do not significantly differ. P-values will be presented for all analyses, but they will be considered descriptive after the first non-significant result is obtained.

Each of the secondary endpoints will be analyzed by the same methods described for the primary efficacy endpoint. Kaplan-Meier estimates, the log-rank test stratified by stratification factors used at randomization, and the Cox proportional hazards model including the stratification factors as specified above for the primary efficacy endpoint, will be summarized by treatment group. In view of the 90-day monitoring period for CV events, the key secondary endpoint for patients who have a non-CV death within 90 days of last contact without having had an earlier CV event will be censored at the time of death. The key secondary endpoint for patients who have a non-CV death more than 90 days after last contact without having had an earlier CV event will be censored at the time of last contact. Kaplan-Meier curves stratified by each stratification factor will be presented. These analyses will be conducted for the ITT population.

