4.7 Efficacy Analyses

4.7.1 Primary Efficacy Endpoint

4.7.1.1 Primary Analysis

The primary efficacy endpoint is the time from randomization to the first occurrence of any component of the composite of the following adjudicated clinical events:

- CV death,
- Nonfatal MI (including silent MI; ECGs will be performed annually for the detection of silent MIs),
- Nonfatal stroke,
- Coronary revascularization,
- Unstable angina determined to be caused by myocardial ischemia by invasive/non-invasive testing and requiring emergent hospitalization.

All observed data that are positively adjudicated by the CEC, including data after discontinuation of study treatment for patients who discontinue study drug prematurely, will be included in the primary analysis.

Suspected endpoint events are adjudicated by the CEC without knowledge of the treatment. Counts and Kaplan-Meier estimates of the percentage of patients experiencing each type of adjudicated event by study completion, along with overall counts for each type, will be presented by treatment arm. A separate table of the number of events that are ruled out by the CEC will also be displayed.

The event time will be calculated as the (date of first event – date of randomization + 1 day) for patients who experience one or more of the primary endpoint events. The following provides detailed considerations for determining the date of event/date of censoring:

- Patients who do not experience a primary efficacy event prior to the end of the study or withdrawal from the study early without a preceding primary efficacy event will be censored at the date of their last visit/phone contact.
- Patients who die with an adjudicated undetermined cause of death and without a preceding endpoint event will be considered to have an adjudicated CV death and this will be included as an event in the primary analysis.

- In view of the 90-day monitoring period for CV events, patients who have a non-CV death within 90 days of last contact without having had an earlier CV event will be censored at the time of death. Patients who have a non-CV death more than 90 days after last contact without having had an earlier CV event will be censored at the date of their last visit/phone contact.
- The primary analysis of silent MI will assume that all silent MIs occurred on the date of the first tracing indicative of a silent MI.

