4.7.3.2 Other Secondary Efficacy Endpoints

Other secondary efficacy endpoints are the time from randomization to the first occurrence of each of the events described below. If the primary and key secondary endpoints are statistically significant, the remaining secondary endpoints will be tested in the following order:

- Composite of CV death or nonfatal MI (including silent MI);
- Fatal or nonfatal MI (including silent MI);
- Non-elective coronary revascularization represented as the composite of emergent or urgent classifications;
- CV death;
- Unstable angina determined to be caused by myocardial ischemia by invasive/non-invasive testing and requiring emergent hospitalization;
- Fatal or nonfatal stroke;
- Composite of total mortality, nonfatal MI (including silent MI), or nonfatal stroke;
- Total mortality.

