6. ANALYSIS OF TERTIARY ENDPOINTS

This section relates to Section 4.7.4 of version 1 of the SAP dated 08 July 2016.

The following clinical events that are positively adjudicated by the Clinical Endpoint Committee (CEC) will be analyzed as tertiary endpoints for the ITT Population:

- Composite of total mortality, or new congestive heart failure (CHF)
- Composite of CV death, or new CHF
- Sudden cardiac death
- Peripheral artery disease (PAD)
- Atrial fibrillation, or atrial flutter

These tertiary endpoints will be analysed similarly as for the primary composite endpoint.

In addition, the following will be analysed as tertiary endpoints for the ITT Population:

- Relationship between on-treatment high-sensitivity C-reactive protein (hsCRP) and the primary and key secondary endpoints
- Relationship between on-treatment serum eicosapentaenoic acid (EPA) and the primary and key secondary endpoints

To assess the relationship between on-treatment hsCRP and the primary and key secondary endpoints, subgroup analyses will be carried out as done for the ITT population for patients grouped according to values greater or equal to or less than 2 mg/dL at baseline and at 2 years.

To assess the relationship between on-treatment serum EPA and the primary and key secondary endpoints, Kaplan-Meier (KM) curves will be produced for AMR101 treated patients grouped into tertiles based on their values at year 1 and will be compared with the placebo-treated patients.

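### SAP 4.7.3 carries the primary endpoint's censoring of non-CV deaths into the two secondary endpoints that count death from any cause

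*Combined protocol and SAP*

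**What the plan says.** SAP 4.7.3 carries the event and censoring rules over in one sentence: "the rules for determining date of event/date of censoring for the primary efficacy endpoint (Section 4.7.1) will be applied to the secondary endpoints". It names no exception.

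The rules carried over are in SAP 4.7.1.1.
- Death soon after contact: a patient with a "non-CV death within 90 days of last contact without having had an earlier CV event will be censored at the time of death".
- Death more than 90 days after last contact: a patient with a non-CV death "without having had an earlier CV event will be censored at the date of their last visit/phone contact".
- Undetermined cause: "Patients who die with an adjudicated undetermined cause of death and without a preceding endpoint event will be considered to have an adjudicated CV death".

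The secondary endpoints are listed in test order in SAP 3.2.1.2 and 4.7.3.2. After the key secondary composite (CV death, nonfatal MI, nonfatal stroke), CV death is fourth of eight. Seventh is "Composite of total mortality, nonfatal MI (including silent MI), or nonfatal stroke", called the all-cause composite below. Total mortality is eighth. Each is tested at the primary endpoint's alpha level (SAP 4.3.6).

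The protocol is narrower. Section 12.2.4.3 attaches the non-CV-death rule to "the key secondary endpoint for patients who have a non-CV death within 90 days of last contact" and mentions no other secondary endpoint. Section 12.2.4.4 extends it to tertiary endpoints only where it applies.

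**The concern.** For most endpoints, censoring a non-CV death is ordinary practice. For an endpoint that counts death from any cause, that death is the event, so an analyst cannot follow both the carry-over sentence and the endpoint definition.

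What two confirmatory tests measure depends on which instruction wins. If the censoring rule wins, total mortality shrinks towards CV death and the all-cause composite towards the key secondary composite. Both counterparts will already have been passed by the time the sequence reaches steps seven and eight. A formal claim on total mortality could then rest on a test that leaves out most non-CV deaths.

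The second limb adds a problem. Protocol 11.2 asks sites to re-contact patients at the end of the trial to establish vital status. A non-CV death found that way, more than 90 days after last contact and with no earlier CV event, would be discarded and the patient censored at the earlier contact. A death of undetermined cause found the same way would count.

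**Working it through.** **1. The plan's own figures.** The documents give no figure for total mortality. The design figures reproduce and are unaffected. A fixed design needs 4(1.960 + 1.282)² / (ln 0.85)² = 1592 events. O'Brien-Fleming-type Lan-DeMets spending at 60%, 80% and 100% gives one-sided levels 0.0038, 0.0110 and 0.0211 and power 0.897 at 1612 events, as in iSAP Table 1. The final critical value is Z = 2.031.

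**2. The rule applied to each kind of death.** Here CV event is taken to mean any primary component.

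| Death | Total mortality by definition | Under the carried-over rule |
|---|---|---|
| CV or undetermined | event | event |
| Non-CV, no earlier CV event, within 90 days of contact | event | censored at death |
| Non-CV, no earlier CV event, after 90 days | event | censored at last contact |
| Non-CV, earlier CV event | event | rule does not reach it |

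The last row is why the result is a near-copy. For the all-cause composite, a patient with an earlier nonfatal MI or stroke already has an event. The only events it adds to the key secondary composite are therefore non-CV deaths after revascularization or unstable angina alone.

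**3. Size.** With CV share s of deaths and fraction k of non-CV deaths preceded by a CV event, the share of all deaths dropped from total mortality is (1 − s)(1 − k). Neither s nor k is in the documents. Assumed annual rates: CV death 1.0%, nonfatal MI or stroke 1.8%, revascularization or unstable angina 2.5%, non-CV death 0.5% to 1.5%. The simulation uses 7990 patients with the plan's accrual pattern and 6.5-year duration, without and with a shared gamma frailty of variance 1.

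| Non-CV rate | Frailty | All deaths | CV | Non-CV | Non-CV kept | Share of all deaths dropped |
|---|---|---|---|---|---|---|
| 0.5% | no | 538 | 359 | 178 | 17 (9.5%) | 30.0% |
| 0.5% | yes | 512 | 338 | 175 | 28 (16.0%) | 28.6% |
| 1.0% | no | 703 | 351 | 351 | 33 (9.4%) | 45.3% |
| 1.0% | yes | 667 | 336 | 331 | 53 (15.9%) | 41.7% |
| 1.5% | no | 867 | 346 | 520 | 50 (9.5%) | 54.3% |
| 1.5% | yes | 812 | 327 | 485 | 76 (15.7%) | 50.3% |

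Simulation error is about one percentage point in the last column. As a hand check on k without frailty, mean entry is 0.2×0.5 + 0.4×1.5 + 0.2×2.5 + 0.19×3.5 + 0.01×4.1 = 1.906 years. Mean follow-up is then about 4.6 years, and a typical death falls near 2.3 years: 1 − exp(−0.043 × 2.3) = 9.4%. The all-cause composite would gain only about 10 to 40 patients over the key secondary composite.

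**4. How near a copy.** The correlation between the CV-death and total-mortality log-rank statistics is roughly √(CV deaths / deaths counted). In the first row this is √(359/376) = 0.98 under the literal rule, against √(359/538) = 0.82 if all deaths count. In the last row it is √(327/403) = 0.90 against √(327/812) = 0.63.

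**5. What a real any-cause test would face.** Assume 600 deaths, s from 0.5 to 0.8, HR for CV death from 0.80 to 1.0, HR for non-CV death 1.0, and critical value 2.031. The mean of Z is m₁ = |ln HR|√(600s)/2 for CV death and m₂ = √s·m₁ for any-cause death, with correlation √s. At s = 0.8 and HR 0.80, m₁ = 2.444 and m₂ = 2.186. The chance that CV death is significant is then 0.660, and the chance that total mortality is significant given that is 0.80. At s = 0.5 and HR 1.0 the conditional chance is 0.33. These figures condition on the CV-death test only, not on the whole sequence.

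**The case against.** The strongest reply is that the carry-over was never meant to override an endpoint's definition. SAP 3.2.1.2 counts the first occurrence of the endpoint's own event type, and any death is that event for total mortality. SAP 4.7.2 uses the same carry-over sentence for the primary components, then adapts it so that only patients without the component event are censored. A wholly literal carry-over also fails for other secondaries, since the first primary rule censors only patients without a primary event. Protocol 12.2.4.3 confines the non-CV-death rule to the key secondary endpoint. On that substitution reading neither limb applies to total mortality, and deaths found late are safe too. With contacts at most 90 days apart, long gaps should also be uncommon. Finally, a false claim needs the primary, the key secondary and at least six other secondaries to succeed first.

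Much of this stands. It shows an internal conflict, and a reader should not infer that the sponsor has settled on censoring non-CV deaths in a mortality endpoint. Nor should a reader infer that total mortality would equal CV death, or that the last two tests would be significant by construction. That holds only if every non-CV death is censored, and the rule reaches only those without an earlier CV event.

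The reply does not remove the defect. The adaptation in SAP 4.7.2 has no counterpart in 4.7.3, and SAP 4.3.1 binds all analyses to the SAP's text. Counting these deaths would be a departure from 4.7.3 as written. The literal reading is no harmless middle course either: a non-CV death would count only after a CV event, an outcome that treatment is expected to change.

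**Conclusion.** Wrong as written. SAP 4.7.3 states a rule that, if followed, censors deaths that two confirmatory endpoints define as events, and it goes beyond the protocol. On the literal reading about 84% to 91% of non-CV deaths, and about 29% to 54% of all deaths, would be dropped from total mortality. Those sizes rest entirely on the assumed event rates, and the true loss depends on a non-CV share that the documents do not give. The last two tests would be near-copies of CV death and the key secondary composite. The primary analysis, the 1612 events, the boundaries and the power are not affected.

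**What to change.** In SAP 4.7.3, limit the non-CV-death censoring rule to endpoints that do not include all-cause death. For total mortality and the all-cause composite, add two statements:

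- Death from any cause up to and including the study end date is an event on its date of death, whatever the gap from last contact.
- For total mortality, patients not known to have died are censored at the last date known alive, including the end-of-study vital-status check and capped at the study end date. Deaths and survivors found by that check are then treated alike.

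Apply the first statement also to the composite of total mortality or new CHF in SAP Addendum section 6, which is to be analysed like the primary endpoint. That composite is exploratory and outside the testing sequence, so this part is for consistency.

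The cost is about two sentences before database lock. No new data are needed, and the change brings the SAP back to the protocol's scope.

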4.7.3.1 Key Secondary Efficacy Endpoint

If the primary analysis is statistically significant, then the key secondary efficacy endpoint, which is the time from randomization to the first occurrence of the composite of CV death, nonfatal MI (including silent MI), or nonfatal stroke will be tested first.

4.7.3.2 Other Secondary Efficacy Endpoints

Other secondary efficacy endpoints are the time from randomization to the first occurrence of each of the events described below. If the primary and key secondary endpoints are statistically significant, the remaining secondary endpoints will be tested in the following order:

- Composite of CV death or nonfatal MI (including silent MI);
- Fatal or nonfatal MI (including silent MI);
- Non-elective coronary revascularization represented as the composite of emergent or urgent classifications;
- CV death;
- Unstable angina determined to be caused by myocardial ischemia by invasive/non-invasive testing and requiring emergent hospitalization;
- Fatal or nonfatal stroke;
- Composite of total mortality, nonfatal MI (including silent MI), or nonfatal stroke;
- Total mortality.

4.7.4 Analysis of Tertiary Endpoints

All tertiary analyses will be conducted for the ITT population. No multiple testing adjustments will be made. Time-to-event tertiary endpoints will be analyzed by the same methods as described for the primary efficacy endpoint. Kaplan-Meier estimates, the log-rank test stratified by stratification factors used at randomization, and the Cox proportional hazards model as specified for the primary efficacy endpoint, will be summarized by treatment group. Kaplan-Meier curves stratified by each of the stratification factors will be presented. Similarly, the rules for determining date of event/date of censoring for the primary efficacy endpoint (Section 4.7.1) will be applied to the tertiary endpoints. The following are the tertiary time-to-event endpoints:

- Total CV events analysis defined as the time from randomization to occurrence of the first and all recurrent major CV events defined as CV death, nonfatal MI (including silent MI), nonfatal stroke, coronary revascularization, or unstable angina determined to be caused by myocardial ischemia by invasive/non-invasive testing and requiring emergent hospitalization;
- Primary composite endpoint in subset of patients with diabetes mellitus at baseline;
- Primary composite endpoint in the subset of patients with metabolic syndrome at baseline as defined in *A Joint Interim Statement of the International Diabetes Federation Task Force on Epidemiology and Prevention; National Heart, Lung, and Blood Institute; American Heart Association; World Heart Federation; International Atherosclerosis Society; and International Association for the Study of Obesity* (Alberti

2009); with cut points of parameters as defined in Table 1 of Alberti *et al.* and waist circumference cut points further guided by Table 2 of Alberti *et al.* and specifically set at ≥ 35 inches (88 cm) for all women and Asian, Hispanic, or Latino men, and ≥ 40 inches (102 cm) for all other men (see [Appendix C](#) in Section 6.3);

- Primary composite endpoint in the subset of patients with impaired glucose metabolism at baseline (Visit 2 FBG of 100-125 mg/dL);
- Key secondary composite endpoint in the subset of patients with impaired glucose metabolism at baseline (Visit 2 FBG 100-125 mg/dL);
- Composite of CV death, nonfatal MI (including silent MI), nonfatal stroke, cardiac arrhythmia requiring hospitalization of ≥ 24 hours, or cardiac arrest;
- Composite of CV death, nonfatal MI (including silent MI), non-elective coronary revascularizations (defined as emergent or urgent classifications), or unstable angina determined to be caused by myocardial ischemia by invasive/non-invasive testing and requiring emergent hospitalization;
- Composite of CV death, nonfatal MI (including silent MI), non-elective coronary revascularizations (defined as emergent or urgent classifications), unstable angina determined to be caused by myocardial ischemia by invasive/non-invasive testing and requiring emergent hospitalization, nonfatal stroke, or PVD requiring intervention, such as angioplasty, bypass surgery, or aneurism repair;
- Composite of CV death, nonfatal MI (including silent MI), non-elective coronary revascularizations (defined as emergent or urgent classifications), unstable angina determined to be caused by myocardial ischemia by invasive/non-invasive testing and requiring emergent hospitalization, PVD requiring intervention, or cardiac arrhythmia requiring hospitalization of ≥ 24 hours;
- New CHF;
- New CHF as the primary cause of hospitalization;
- Transient ischemic attack (TIA);
- Amputation for PVD;
- Carotid revascularization;
- All coronary revascularizations defined as the composite of emergent, urgent, elective, or salvage;
- Emergent coronary revascularizations;
- Urgent coronary revascularizations;
- Elective coronary revascularizations;
- Salvage coronary revascularizations;
- Cardiac arrhythmias requiring hospitalization of ≥ 24 hours;

- Cardiac arrest;
- Ischemic stroke;
- Hemorrhagic stroke;
- Fatal or nonfatal stroke in the subset of patients with a history of stroke prior to baseline;
- New onset diabetes, defined as Type 2 diabetes newly diagnosed during the treatment/follow-up period;
- New onset hypertension, defined as blood pressure ≥ 140 mmHg systolic OR ≥ 90 mmHg diastolic newly diagnosed during the treatment/follow-up period;
- Fasting TG, TC, LDL-C, HDL-C, non-HDL-C, VLDL-C, apo B, hs-CRP (hsCRP and $\log[\text{hsCRP}]$), hsTnT, and RLP-C (to be estimated from standard lipid panel, $\text{RLP-C} = \text{TC} - \text{HDL-C} - \text{LDL-C}$ [Varbo 2014]) (based on ITT estimands):
 - Assessment of the relationship between baseline biomarker values and treatment effects within the primary and key secondary composite endpoints,
 - Assessment of the relationship between post-baseline biomarker values and treatment effects within the primary and key secondary composite endpoints by including post-baseline biomarker values (for example, at 4 months, or at 1 year) as a covariate.

Continuous tertiary endpoints include:

- Change from baseline and percent change from baseline in fasting TG, TC, LDL-C, HDL-C, non-HDL-C, VLDL-C, apo B, hs-CRP (hsCRP and $\log[\text{hsCRP}]$), hsTnT, and RLP-C (to be estimated from standard lipid panel, $\text{RLP-C} = \text{TC} - \text{HDL-C} - \text{LDL-C}$ [Varbo 2014]) (based on ITT estimands);
- Change in body weight;
- Change in waist circumference.

The fasting lipid panel is tested at Screening (Visit 1 or Visit 1.1), Randomization visit (Visit 2; Day 0), Visit 3 (Day 120; ~4 Months) and all other follow-up visits including the last visit. For change from baseline to 1-year Preparative Ultracentrifugation measurements for LDL-C will be analysed, unless this value is missing. As described in Section 4.3.3, if the LDL-C Preparative Ultracentrifugation values is missing, then another LDL-C value will be used, with prioritization of values obtained from LDL-C Direct measurements, followed by LDL-C derived by the Friedewald calculation (only for subjects with TG < 400 mg/dL), and finally LDL-C derived using the calculation published by Hopkins University investigators (Martin 2013). In addition, change from baseline to day 120 in LDL-C utilizing Friedewald's and Hopkins methods will be analysed, using the arithmetic mean of LDL-C obtained at Visit 2 (Day 0) and the preceding Visit 1 (or Visit 1.1). If one of these values is missing, the single available LDL-C value will be used. LDL-C according to Hopkins will be calculated at each visit.

The randomization visit will be considered Baseline. If a baseline value is not available from the randomization visit, then the latest screening value will be used.

For measurements of lipids, lipoproteins, and inflammatory markers, the change from baseline and the percent change will be summarized at each visit. Since these parameters are typically not normally distributed, the Wilcoxon rank-sum test will be used for treatment comparisons of the percent change from baseline, and medians and quartiles will be provided for each treatment group. The medians of the differences between the treatment groups and 95% CIs will be estimated with the Hodges-Lehman method. In addition, shift-tables may be generated as appropriate.

As an additional exploratory analysis, the relationship between post-baseline biomarker values and treatment effects with the primary and key secondary composite endpoints will be assessed by adding biomarker values (for example, at 4 month, or at 1 year, etc.) as time-dependent covariates in the Cox proportional hazards model. Diagnostic plots for the proportional hazards assumption will be evaluated.

Weight is measured at the screening visit and at all follow-up visits, including the last visit of the study. Waist circumference will be measured at the randomization visit (Visit 2; Day 0), Visit 5 (Day 720) and the last visit of the study. Descriptive statistics will be presented by visit and treatment group for baseline, post-treatment change from baseline, and the percent change from baseline. Analysis methods for repeated measurements will be used to compare percent change from baseline between treatments.

